### **Risks, adverse events and disadvantages**

LVA is considered a safe and valid treatment for lymphedema. (3,40,41)

There are already well-established centres in Europe, USA and Australia, offering surgical treatment for breast cancer related lymphedema. However, studies present different results regarding the decrease in arm volume, reaching from insignificant to significant. (6,7,24) Even so, as previously described, surgical treatment seems effective in selective patient groups, but systematic studies for this are lacking. (2,10,11,25,26)

As in any surgery, there will be a small scar from the surgical incision, which tend to fade over time. (42) Other potential, general adverse events include wound problems, bleeding, infection and cardio vascular events such as thrombosis. The overall risk of a severe and fatal events occurring during surgery is generally small. (43) Adverse effects specific for the LVA procedure includes worsening of the patient's lymphedema. (2,40,44) A review with a safety assessment for the LVA procedure found no reported serious adverse events based on 217 included studies. Otherwise skin irritation was found as an adverse event of the site of contrast injection in two

patients (10%). (41) In case of a known or unknown adverse event, or adjacent pain, relevant treatment will be initiated.

The ICG lymphangiography is considered both safe and easy to perform. The patient might experience minor discomfort when injecting dye intradermal into the hand. In order to ease this discomfort, patients are numbed using infiltration of lidocaine at the site on injection. Patients undergoing the clinical assessment, will be monitored 60 minutes after the injection for an allergic reaction caused by the dye applied, including anaphylactic shock. In case of an allergic or anaphylactic incidence, relevant treatment will be initiated. (32)

The LVA procedure is considered minimally invasive, but based on the duration of the operation, the surgery will be performed under general anesthesia.

Patients generally experience minimal pain after surgery. If this is not the case, appropriate pain treatment will be given. (45)

### **Collection of Data**

Pre-operative: The patients will be examined in the outpatient clinic by the primary investigator. Circumference tape measurement and water displacement will be executed for volume quantification of both arms, in addition to bioimpedance for measurements of L-Dex score and body composition. A questionnaire regarding quality of life in relation to living with lymphedema, LYMPH-Q, will also be completed prior to the intervention.

ICG lymphography will subsequently be performed by the operating surgeons and the primary investigator for mapping of lymphatic vessels. (33,34)

Ultra high frequency ultrasound will be used for mapping veins adjacent to the lymphatic vessels for anastomosis. The number of vessels and their location for anastomosis will be registered and mapped prior to surgery.

Video recordings of the ICG lymphography is performed for staging of lymphedema. Photos of the patient's arms will be recorded as well.

During surgery: The number of actual applicable lymphatic vessels and venous veins found during surgery will be registered, and also whether these were usable for anastomosis.

3 months post-operative follow-up: Patients will be examined in the outpatient clinic for circumference tape measurement and water displacement for volume calculation of both arms, in addition to bioimpedance for measurements of body composition and L-Dex score, in addition to ICG lymphangiography. The patients will be asked to complete the LYMPH-Q questionnaire once again.

Cases of adverse side effects will be collected continuously.

Collected data provides the following for comparison, as previously described:

- 1) The primary outcome is comparison of the number of lymph vessels and venules found during surgery and the number originally planned.
- 2) Arm-volume measurements for each patient will form the basis for calculating the volume difference between the patient's arms. The volume difference before and after surgery will be compared. This applies to data collected from both manual measurements and water-displacement test.
- 3) Comparison of ICG lymphography video recordings before and 3 months after intervention, with changes in MD Anderson classification system of lymphedema.
- 4) Changes in LYMPH-Q scores for each individual scale from before and 3 months after intervention.
- 5) Changes in L-Dex score measured by stand-up bioimpedance before and 3 months after surgery. (38,39)
- 6) Changes in measurements of body compositions before and 3 months after LVA surgery.

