### **Material and methods**

[figure not shown]
ICG lymphography is a technique for visualization of the superficial lymphatic systems. By injecting ICG subcutaneously, it enables a real-time visualization of the lymphatic networks through a minimally invasive procedure. ICG is a non-toxic tracer with low risk of complications; 0.17% risk in general, and 0,02% for nonsevere shock, by intravenous injection. Severe allergic reaction, including anaphylactic shock, affects fewer than 1/10.000 patients. (32,33)

The ICG lymphography is performed and used for visualisation of the superficial lymphatics for preoperative planning, using 0.1 mL ICG (2.5 mg/mL Verdye, Diagnostic Green, Ascheim, Germany). The dye is injected subcutaneously at the wrist, near the ulnar border of the palmaris longus tendon, and in the 1st and 3rd web space of the hand. Scans are performed using an infrared camera, the HyperEye medical system (MNIRC-501, HEMS; Mizuho Co., Tokyo, Japan). During real-time visualization, lymphatic vessels are drawn up on the patients arm using a permanent marker. (32,34)

Ultra high frequency ultrasound (>30MHz) has the ability to visualize small, superficial anatomical layers. (10,30,35) Using this ultra high frequency ultrasound, following the mapped lymphatic vessels, venous vessels are found nearby and likewise mapped for anastomosis. The ultrasound scans are performed using a 70MHz probe (Vevo® MD Imaging System, Fujifilm, VisualSonics Inc.). The number of LVA anastomosis sites is set to a minimum of two sites per extremity. The number of mapped lymphatics vessels and venoles are compared to the number identified during surgery and recorded.

The secondary outcomes includes: 1) changes of arm volume over time, 2) changes of lymphatic flow pattern before and after surgery by ICG lymphangiography, 3) changes in health-related quality of life by the use of the LYMPH-Q questionnaire and 4) changes in L-Dex score and body composition measured with bioimpedance before and 3 months after LVA surgery. (32,36,37,37–39)

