Collected data includes the patients name, social security number, age, height and weight, BMI, gender, breast cancer diagnosis, treatment prior to the study in relation with their breast cancer diagnosis, duration and stage of lymphedema in upper extremity, number of mapped and applicable vessels pre- and per-operatively, number of anastomosis made during surgery, number of days of hospitalization, operation description, description of admission, name of the operators, pictures, videos and measurements from before, during and after the surgery, known allergies, medicine list, smoking status and any side effects or complication related to the surgery or 3 months after.

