### **Feasibility**

The pre-graduate student is responsible of writing the protocol for this study, provide necessary funding, participate in patient inclusion and examinations and assist during surgery, carry out the data analysis, and writing the article. The Department of Plastic Surgery OOUH offers office facilities. Both supervisors provide necessary knowledge and experience to conduct this project within one year.

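### For the ICG-mapped lymphatics, the primary mapped-versus-found comparison has no reference reading independent of the map, so agreement is at risk of upward bias

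*Protocol*

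**What the plan says.** Collection of Data defines the endpoint: "The primary outcome is comparison of the number of lymph vessels and venules found during surgery and the number originally planned". The Introduction gives the aim as testing whether neighbouring lymphatics and venules can be identified correctly before surgery, so the map is the test and the surgical finding is its reference.

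- **Who maps the lymphatics** (Collection of Data): "ICG lymphography will subsequently be performed by the operating surgeons and the primary investigator for mapping of lymphatic vessels".
- **Who maps the venules** (Collection of Data): "Ultra high frequency ultrasound will be used for mapping veins adjacent to the lymphatic vessels for anastomosis". No operator is named.
- **Visibility of the map** (Material and methods): "lymphatic vessels are drawn up on the patients arm using a permanent marker". Venules found along these lines are mapped too.
- **The surgical reading** (Collection of Data): "The number of actual applicable lymphatic vessels and venous veins found during surgery will be registered, and also whether these were usable for anastomosis". No assessor is named.
- **The investigator's other roles**: the Feasibility section has the student "participate in patient inclusion and examinations and assist during surgery, carry out the data analysis". The Publication Plan names the student as primary investigator, and the Database section has the primary investigator enter the data.
- **Other surgical records** (Database): the number of anastomoses made, the operation description, and "pictures, videos and measurements from before, during and after the surgery".

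**The concern.** When a test is checked against a reference reading, that reading should not depend on knowledge of the test result. Here the operating surgeons expose lymphatics that they helped to mark, with the marks in view. Whether a small vessel counts as found or applicable is partly a judgement. The eligibility table uses the word *applicable* for vessels seen before surgery, and Collection of Data uses it again for vessels seen at surgery. Neither place defines it. People who drew a map tend to confirm it, so the likely direction is towards agreement, which favours the combined imaging method.

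A comparison of two numbers adds a related weakness. An unmapped vessel met by chance can stand in for a mapped vessel that was not there, and the totals still agree.

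This is the only primary outcome. Sample size and Statistics says that positive results would form the basis of a further clinical study, and the Background hopes for an algorithm for choosing between surgery and other treatment. Who makes the reference call, when, and on what evidence is data-collection design, and no later analysis can supply it.

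**Working it through.** The protocol gives no agreement rate and no calculated sample size, so there is no planned figure to reproduce. The check has two parts.

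**1. Independence, from the text**

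| Step | Who, according to the protocol | Overlap with the map |
|---|---|---|
| ICG mapping of lymphatics | Operating surgeons and primary investigator | This is the map |
| Ultrasound mapping of venules | Not stated | Cannot be judged |
| Exposure of vessels | Operating surgeons, with the investigator assisting | Explicit for lymphatics |
| Found, applicable or usable call | Not stated | Strong inference only |
| Data entry and analysis | Primary investigator | Explicit |

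No section provides a reading by anyone outside the mapping. No section links the intra-operative pictures and videos to the primary comparison.

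**2. Scale, as an illustration**

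Inputs from the protocol: 10 patients (Design and population), at least two anastomosis sites per extremity (Material and methods), and one lymphatic joined to one venule (Design and population).

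- Sites: 10 × 2 = 20 at the minimum.
- Vessels: 20 lymphatics + 20 venules = 40 at the minimum, if each site contributes one pair.
- Weight of one call: 1/20 = 5 points if sites are scored as pairs or each vessel type is reported separately; 1/40 = 2.5 points if all vessels are pooled. The protocol does not fix the unit.

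Exact (Clopper-Pearson) 95% intervals, with sites treated as independent:

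- 16/20 = 80% (56.3 to 94.3)
- 18/20 = 90% (68.3 to 98.8)

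Two lenient calls thus move the estimate by 10 points on the paired scale. The interval around 16/20 is 94.3 − 56.3 = 38 points wide, so a shift of that size could not be seen in the data.

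Let p be the true share of mapped vessels that are present, f the share of absent vessels called found, and g the share of present vessels missed. The reported share is p(1 − g) + (1 − p)f. All three values below are assumptions.

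- p = 0.70, g = 0, f = 0.10: 0.70 + 0.30 × 0.10 = 0.73
- p = 0.70, g = 0, f = 0.25: 0.70 + 0.30 × 0.25 = 0.775
- p = 0.70, g = 0, f = 0.50: 0.70 + 0.30 × 0.50 = 0.85
- p = 0.90, g = 0, f = 0.50: 0.90 + 0.10 × 0.50 = 0.95
- p = 0.70, g = 0.05, f = 0.10: 0.70 × 0.95 + 0.30 × 0.10 = 0.665 + 0.030 = 0.695

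The last line shows that the net error need not be upward once missed vessels are allowed for.

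**The case against.** The strongest reply has five parts.

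1. **Surgeons must see the map to operate.** This stands. Masking the surgeon to location is not realistic, and the fix does not ask for it.
2. **The protocol does not say that the mappers make the call.** This stands. It says only that vessels will be registered, and the ultrasound operator is unnamed. A reader might infer that the same people map and judge both vessel types. The overlap of mapping and operating is documented only for the ICG-mapped lymphatics, and venules are the other part of the endpoint.
3. **Upward bias is not shown.** This stands. A reader might infer that the result is biased upward. The documents support only a risk: the size is unknown, and the last line of the calculation goes the other way.
4. **The calls can be checked in part.** This stands. A reader might infer that a lenient call leaves no trace, but planned locations, the number of anastomoses, the operation description and intra-operative images are all collected. Each completed 1:1 anastomosis is firm evidence of one lymphatic and one venule. It does not cover vessels called found but not joined, and a bare count does not show that the joined vessel was the one mapped.
5. **This is a hypothesis-generating pilot with no success threshold.** This lowers the weight of the point. It does not remove it, because the comparison is the study's primary aim and a further study depends on its result.

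**Conclusion.** The point holds as a risk. For the ICG-mapped lymphatics, the reference reading of the primary outcome is not independent of the map, and the undefined term *applicable* leaves room for lenient calls. The likely direction is towards agreement, and the exposure lies mainly in vessels called found but not anastomosed. The documents do not establish that bias will occur, how large it would be, or that it extends to the venules.

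On the minimum of 20 paired sites, each call is worth 5 points; on at least 40 pooled vessels, 2.5 points. These figures assume the minimum number of sites, one pair per site, and independence of sites within a patient. The 16/20 and 18/20 results and the values of p, f and g are illustrations and not protocol figures.

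The change should be made before enrolment, or for the remaining patients if enrolment has begun. It is proportionate for a pilot because it uses material that the protocol already collects.

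**What to change.** In Collection of Data:

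1. **Before surgery:** number every mapped lymphatic and venule, and lock the map in REDCap. Name the role that performs the ultrasound mapping.
2. **During surgery:** at each site, before any anastomosis is decided, record found or not found and usable or not usable for each numbered vessel, against a one-line criterion set in advance. Record unmapped vessels separately. Name the role that makes the call.
3. **Evidence:** link one intra-operative still or clip to each call, from the pictures and videos already listed under Database.
4. **Primary outcome:** state that the comparison uses these per-vessel calls, and whether lymphatics and venules are reported separately, as pairs or pooled.
5. **Independence:** where more than one surgeon is on the case, have the call made by one who did not draw that patient's map, if roles can be split without added staff. The protocol has the operating surgeons do the mapping and does not guarantee such a person, so otherwise report the lack of independence as a limitation.

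The cost is protocol wording, a short REDCap form and a few minutes per site. No visit or procedure is added. The marks stay visible, so the fix makes the calls timed and checkable but does not make the reading fully independent.

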## **Background**

Breast-cancer related lymphedema is a life-disabling side-effect of breast cancer treatment, affecting more than 1 in every 5 patients. (12,13) With breast-cancer being the most common cancer diagnosis in women, affecting up to 2.3 million new cases globally, and with a generally high survival rate of 80% or higher in developed countries, the number of breast-cancer survivors with long-term sequela is significant. (14,15) In 2020, 5083 patients were diagnosed with breast cancer in Denmark, which based on the incidence, gives an estimated number of 800 or more of these patients will develop lymphedema per year. (16)

Due to a disruption to the lymphatic system with inadequate drainage, protein-rich lymph fluid is accumulated in the interstitial tissue, causing excessive swelling of the upper extremity, breast, and truncus of the treated side. (17) This accumulation of fluid promotes chronic inflammation in

the extracellular matrix and fibrosis and hypertrophy of the adipose tissue, followed by annihilation of the lymphatic vessel lumen due to sclerosis. (8)

Compression garments and physiotherapy have been considered the standard treatment and rehabilitation for lymphedema. (18) Some of the disadvantages with these treatments include variability in patient compliance, clinical effect and lack of statistical significant results. (19)

As breast cancer is the most common cancer among women, with an increasing survival rate due to improved treatment, the rehabilitation and treatment options for long-term sequela are in high demand, affecting patients physical and mental health. (2–6,20–22)

These long-term sequelae include swelling, arm heaviness, tightness, pain, weakness and affected functionality of the arm. Moreover, breast-cancer survivors with breast cancer related lymphedema report emotional sequelae, including deterioration of generic mental health, social role functioning, life and social activities and bodily pain. (1,20,22) In addition to this, the condition generally worsens over time, emphasizing the need for long-term treatment of lymphedema.(18,23)

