#### Quality of life

The LYMPH-Q Upper extremity module questionnaire is a validated patient-reported outcome tool for women with breast cancer related lymphedema. The module contains seven individual scales, measuring: symptoms, function, appearance, psychological function, and satisfaction with

information on lymphedema and satisfaction with arm sleeve. Each scale gives an independent score, which can be used for comparison of change over time. (37)

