### **Database**

OPEN REDCap – Research Electronic Data Capture, will be applied for a secure storage of all data. REDCap is a worldwide online system developed for non-commercial clinical research. Data will be stored on OPEN's servers in the Region of Southern Denmark. Here, data is entered via an encrypted connection and meets current data protection requirements. The database will primarily be used to enter and store clinical data, as well as a few simple calculations based on these clinical data, for example BMI calculation. Only members of the research group will have access to this database. No contractual agreement that limits this access, is relevant.

As a starting point, the database will exist until the 31st of January 2024. As the study is a pilot study, there is, however, the possibility of extension with the inclusion of several test subjects for further exploratory study.

Objective measured data, as well as any general personal data that does not already appear in the patient journal, will originally be collected by the primary investigator during the examination.

Collected data and data from the patient's record is then transferred to the REDCap database by the primary investigator. Written informed consent for participating in the project, including collecting information from the patient's examination and journal, is obtained at the patients' first consultation in the outpatient clinic. Only patients who provide written, informed consent is enrolled in the project. No data is collected nor known to the researcher prior to this.

The consent gives the trial supervisor, sponsor and sponsor's representatives as well as any control authority direct access to obtain information in the patient's medical record, as part of the implementation of the research project as well as for control purpose.

The LYMPH-Q questionnaire is completed prior-to and 3 months after the intervention on paper form, which is subsequently entered into the REDCap database by the medical student.

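### Concurrent compression and physiotherapy are not recorded at 3 months, and the ICG videos are staged with no step that hides the visit, so the uncontrolled secondary changes are harder to read than they need to be

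*Protocol*

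**What the plan says.** The Design and population section describes a hypothesis-generating pilot of 10 patients who all receive LVA and are followed for 3 months, with no comparison group. The secondary outcomes are changes from before surgery to 3 months after.

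**Co-treatment.** The Background states that "Compression garments and physiotherapy have been considered the standard treatment and rehabilitation for lymphedema" and lists among the disadvantages "variability in patient compliance, clinical effect and lack of statistical significant results". The visit procedures in Collection of Data consist of tape measurement, water displacement, bioimpedance, ICG lymphography and LYMPH-Q. For the 3-month visit the text reads "Patients will be examined in the outpatient clinic for circumference tape measurement and water displacement for volume calculation of both arms", followed by the other measurements. The data list under Database includes "treatment prior to the study in relation with their breast cancer diagnosis". The same section says that "any general personal data that does not already appear in the patient journal, will originally be collected by the primary investigator during the examination". In the Quality of life section, LYMPH-Q covers satisfaction with "information on lymphedema and satisfaction with arm sleeve".

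**Arm volume.** Collection of Data, comparison item 2: "Arm-volume measurements for each patient will form the basis for calculating the volume difference" between the arms, which is then compared before and after surgery. Item 5 compares L-Dex before and after.

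**ICG stage.** Classification of lymphedema says that recordings are kept and staged later on the MD Anderson scale (0 to 5), by recognising dermal backflow patterns. Collection of Data, item 3, is "Comparison of ICG lymphography video recordings before and 3 months after intervention", with the change in stage as the result. No reader, reading order or masking is stated.

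**The concern.** Without a control group, a before/after change can be read only against what else changed in the same period. The protocol itself identifies compression and physiotherapy as the usual treatment and says that adherence varies. If a patient uses more or less of either on the affected arm after surgery, her volume difference and L-Dex may move for that reason, and the study data would give no sign of it. Use that nobody asked about at the visit cannot be supplied later by an analysis plan.

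Stage is a judgement on an ordinal scale. A reader who knows which clip is post-operative may settle a borderline case in the expected direction.

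Sample size and Statistics and Impact both make a larger study depend on positive results, and Impact expects knowledge on what LVA does. The secondary changes may therefore be carried into later planning.

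**Working it through.** The plan gives no figure to reproduce. Its 10 patients rest on feasibility, with no SD, expected change or reader agreement. The check is mainly a comparison of sections.

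**1. Is concurrent co-treatment recorded?**
- Collection of Data, pre-operative and 3-month procedures: no item.
- Database, data list: the nearest item is "treatment prior to the study in relation with their breast cancer diagnosis". The lymphedema studied is a consequence of breast cancer treatment, so a broad reading could take in earlier lymphedema care. Even so, it stops at study entry.
- Patient journal: this may show prescriptions or referrals, but probably not actual use, and no section plans to extract it.
- LYMPH-Q: satisfaction with the sleeve, not hours worn.
- Apart from that sleeve scale, the body text does not return to compression or physiotherapy after the Background.

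Result: at most a partial record at baseline and none at 3 months. A change in use cannot be formed.

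**2. Does the between-arm difference deal with it?** Write D = V(affected) − V(other). A change c common to both arms gives (V(affected) + c) − (V(other) + c) = D, so it cancels. A change t in the affected arm alone gives D + t, so it remains.

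**3. Is the visit hidden from the reader of the videos?** Classification of lymphedema and item 3 give the method and the comparison but no masking. Collection of Data says that the operating surgeons and the primary investigator perform the mapping lymphography. Publication Plan identifies the primary investigator as the student, and Feasibility has the student examine patients, assist at surgery and analyse the data. Those closest to the videos would therefore know the visit. Material and methods has vessels drawn on the arm in permanent marker, and Design and population places videos and pictures after mapping. Marker lines, as well as later scars, may thus reveal the visit.

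**4. Illustration of size (all of k, d and m are assumptions).** Suppose k of 10 patients change co-treatment in the same direction and each shifts by d SD of the change score. The mean change then moves by k × d / 10.

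| | k = 1 | k = 3 | k = 5 |
|---|---|---|---|
| d = 0.5 | 0.05 SD | 0.15 SD | 0.25 SD |
| d = 1.0 | 0.10 SD | 0.30 SD | 0.50 SD |

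The 95% half-width for a mean change with n = 10 is t(0.975, 9)/√10 = 2.262/3.162 = 0.715 SD. To reach it, k must be 0.715 × 10/1.0 = 7.15, that is 8 patients, at d = 1.0. At d = 0.5, k would be 14.3, which is more than the 10 enrolled.

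For stage, if m borderline pairs are read one stage lower after surgery and the other pairs are unchanged, the share improved is m/10 and the mean stage moves by −m/10. With m = 3, 0 of 10 (exact 95% CI 0 to 30.8%) becomes 3 of 10 (6.7 to 65.2%), and the mean stage moves by −0.3.

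**The case against.** The strongest reply is that nothing in the protocol is stated wrongly: it neither claims to control co-treatment nor promises masked reading. The data list is introduced as what the data include, so it may not be complete, and the forms are not shown. A reading manual may settle who reads the videos and how. The study is a pilot with no power claim, and its primary outcome is vessel mapping.

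Much of this stands, and it rules out several stronger readings that a reader might infer:
- *That baseline use is not recorded at all.* The prior-treatment item and the journal may capture part of it. Only the 3-month gap is firm.
- *That the student or a surgeon stages the videos.* No section says so; the overlap of roles only shows why masking is worth stating.
- *That recording use would separate the effect of LVA from that of co-treatment.* With 10 patients and no control it would not, and use at 3 months may itself follow from surgery.
- *That the protocol overclaims and needs rewording.* Design and population and Sample size and Statistics already call the study hypothesis generating.
- *That the carry-forward is certain.* Positive results is not defined and may refer to mapping.

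What the reply does not answer is that co-treatment at 3 months has to be asked about at the visit if it is to be known. Nor does it answer that the protocol describes how staging is done and leaves out a masking step that stored videos make easy.

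**Conclusion.** The point holds for secondary outcomes only. Arm volume (both methods) and L-Dex lack the co-treatment context needed to read an uncontrolled change, and ICG stage lacks a stated safeguard against reader expectation. The comparison of planned with found vessels is unaffected.

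The size of any bias cannot be derived from the document. On the assumed ranges above, a co-treatment shift would usually be modest and smaller than the sampling uncertainty at n = 10, but it would be a bias that the confidence interval does not show. A few borderline readings could change the apparent share with improved stage. A reader might infer that the reported changes will be biased; the document supports only that such a bias could not be seen. Severity is low to moderate, and the case for acting rests on the very low cost.

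**What to change.** 1. In Collection of Data and in the Database data list, add self-reported compression use (hours per day) and physiotherapy (number of sessions) at baseline and at 3 months, with no change to care. List both per patient beside the change in volume and L-Dex. State that this is description, not adjustment, and does not allow attribution to LVA.
2. In Classification of lymphedema, state that the stored videos are coded and staged in random order with patient and visit hidden. Clips should be prepared as far as possible so that marker lines and scars do not reveal the visit. The reader should preferably be a member of the existing team who did not take part in that patient's surgery.

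Cost: two form fields at two planned visits (10 × 2 = 20 visits) and the coding and preparation of about 20 videos. No extra visit or procedure is needed. Self-reported use is imprecise, and masking will be imperfect in so small a group, but both improve on what is now stated.
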